5.2 PROCEDURES

5.2.1 OVERVIEW OF STUDY PROCEDURES

Using the CRF, the investigator will interview both conscious cases and witnesses. For cases who are unconscious or unable to communicate, the medical file will serve as a source of information. Blood samples for cases and controls will be taken on D1 of the study.

5.2.2 STUDY/VISIT SCHEDULE

5.2.2.1 Day 1: main study visit

Participants will be informed of the study's objectives and design; if they agree, an informed consent form will be signed. After inclusion, the main study procedures will take place (questionnaire, sampling and follow-up).

The following variables will be collected:

- **Socio-demographic variables :**

- Age
- Gender
- Profession
- Civil status
- Study level

- **Medical history**

PROTOCOL: MALARIA AS A PROTECTIVE FACTOR AGAINST SEVERE COVID-19 IN THE DEMOCRATIC REPUBLIC OF CONGO

- Comorbidities: diabetes, tuberculosis, cancer, HIV, renal failure, chronic liver disease, chronic lung disease, heart disease
- Medicines
- Smoking
- Pregnancy
- **Clinical variables :**
 - Clinical status according to WHO scale
 - Duration of symptoms
 - Type of symptoms
 - Size
 - Weight
 - Blood Pressure
 - Heart Rate
 - Respiratory Rate (RR)
 - Temperature (T°)
 - Free Oxygen Saturation (SaO)₂
 - Spleen size

The following biological samples will be collected:

- 30 ml of venous blood will be collected using Lithium-Heparin vacutenaire tubes for the various immunological analyses (described below).
- 5 µl of capillary blood will be taken for the thick smear, two µl of blood for the thin smear (GE/FM) and one drop of blood for the TDR.

The results of the thick drop and RDT will be communicated to the attending physicians for hospitalized patients (cases). For outpatients (controls), the results will be communicated to the ZS team in charge of malaria management, in accordance with national guidelines.

Day 7 +- 2: follow-up

For controls: a telephone contact on Day 7 with the treating clinician or the patient will be considered in order to obtain information on their clinical evolution. If, in the meantime, they have developed severe COVID-19, they will be excluded from the study and will no longer be considered as controls.

During participation in the study, the telephone number of the control as well as that of a close relative and the attending physician will be recorded in order to monitor the participant's health status. The patient's telephone number will be recorded separately in the patient identification register, which will be accessible only to local investigators. This

PROTOCOL: MALARIA AS A PROTECTIVE FACTOR AGAINST SEVERE COVID-19 IN THE DEMOCRATIC REPUBLIC OF CONGO

number will not be included in the CRF or patient recruitment register. If no telephone contact is possible, a home visit by the control will take place at D7.

5.2.3 LABORATORY PROCEDURES.

All analyses will be carried out by the INRB laboratory in Kinshasa.

30 ml of venous blood will be collected using Lithium-Heparin vaccutenaire tubes. After centrifugation, the plasma fraction will be stored at -80°C and subsequently used to determine antibodies against malaria and COVID-19 using Luminex. A Luminex test will be developed specifically to determine the following *Plasmodium* antigens: CSP, AMAI, CSPM, GLURP, Pf/RESA55 and SARS-CoV-2 antigens. In the unlikely event of it not being possible to install the Luminex test in Kinshasa, a commercial ELISA test will be used as an alternative.

The PBMC fraction will be isolated for ELISPOT assays with malaria and SARS-CoV-2 antigens and *in vitro* experiments on entrained immunity, and the remainder cryopreserved afterwards. The potency of cellular immunity against Plasmodium and SARS-CoV-2 will be measured by IFN- γ ELISPOT assays. In a subgroup of individuals, flow cytometry measurements may be performed to validate the functionality and phenotype of responding cells.

For experiments on trained immunity, the PBMC fraction will be stimulated with ligands specific to antiviral receptors of the innate immune system (TLR3, TLR7-9, RIG-I, MDA-5, cGAS) [18]. The release of antiviral cytokines (e.g. type I IFN, CXCL10) will be measured by commercial ELISAs and multiplexed flow cytometry assays.

In addition, 5 μ l of capillary blood will be taken for the thick smear, two μ l of blood for the thin smear (GE/FM) and one drop of blood for the TDR.

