5.1.1 INCLUSION CRITERIA

To be eligible, study patients must meet the following criteria:

For cases :

- Must be at least 18 years old
- RT-PCR-confirmed SARS-CoV-2 infection no more than 72 hours prior to inclusion.
- Have given their informed consent or that of their guardian/representative to participate in the study.
- Diagnosed as severe COVID-19 according to the following criteria:
 - Clinical signs of pneumonia: fever, cough, dyspnea or crepitations
AND
 - Presenting at least one of the following signs:
 - Respiratory rate > 30 cycles/min
OR
 - Severe respiratory distress or SpO2 < 90% on room air

PROTOCOL: MALARIA AS A PROTECTIVE FACTOR AGAINST SEVERE COVID-19 IN THE DEMOCRATIC REPUBLIC OF CONGO

- Being admitted to a care unit for COVID-19
- Have lived in the health zone for at least 6 months

For witnesses :

- Must be at least 18 years old
- PCR-confirmed SARS-CoV-2 infection within 72 hours of inclusion.
- Have given informed consent to participate in the study
- Diagnosed as a non-severe COVID-19 case according to the following criteria:
 - Be asymptomatic

OR

 - Symptomatic, but no signs of severe pneumonia
 - Respiratory rate > 30 cycles/min

OR

 - Severe respiratory distress or SpO2 < 90% on room air
- Not to be admitted to a care unit for COVID-19.
- Have lived in the study area for at least 6 months

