5.1.3 RECRUITING SEVERE CASES

Severe cases will be recruited from four state CTCOs. The choice of CTCOs takes into account the frequency of severe cases and the geographical distribution of malaria in the city of Kinshasa. The centers are as follows:

- Saint Joseph Hospital
- Kinkole General Hospital
- Cliniques Universitaires de Kinshasa
- Ngaliema Clinics

PROTOCOL: MALARIA AS A PROTECTIVE FACTOR AGAINST SEVERE COVID-19 IN THE DEMOCRATIC REPUBLIC OF CONGO

After political and administrative authorizations have been obtained by a qualified member of the research team, all severe cases in the care units of the selected centers will be investigated for their eligibility for the study, and then invited to participate and give informed consent.

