4. VARIABLES OF INTEREST**4.1. PRIMARY VARIABLES OF INTEREST :**

The primary variable of interest in the study is the level of anti-malarial antibodies in severe and non-severe COVID-19 cases. This level will be assessed by measuring the concentration of IgG against Circum Sporozoite Protein (CSP) using the Luminex-MAGPIX.

4.2. SECONDARY VARIABLES OF INTEREST :

- Anti-malarial IgG antibody levels against other antigens: AMAI, CSPM, GLURP, *Pf/RESA55*, as well as IgM antibodies

- Cellular response against malaria between severe and non-severe COVID-19 cases, measured by IFN-γ ELISPOT
- The proportions of acute malaria infection between severe and non-severe cases of COVID-19 using the Thick Gauge (TG) and Rapid Diagnostic Test (RDT). Indicator variables will be used for a positive RDT result, for a positive EW result and for a positive result with both tests
- Clinical features :
 - Duration of symptoms
 - Type of symptoms
 - Size
 - Weight
 - Blood pressure
 - Heart Rate
 - Respiratory Rate (RR)
 - Temperature (T°)
 - Free Oxygen Saturation (SaO2)
 - Splenomegaly

and clinical status of severe and non-severe cases of COVID-19 with and without malaria.

The clinical status of COVID-19 only controls is assessed by the WHO 10-point clinical progression score at 7^{ème} days of follow-up¹ :

Patient's condition	Description	Score
Not infected	Not infected; no viral RNA detected	0
Ambulatory: illness benign	Asymptomatic; viral RNA detected	1
	Symptomatic; independent patient	2
	Symptomatic; need for assistance	3
Hospitalized: moderate illness	Hospitalized; no oxygen therapy	4
	Inpatient; oxygen therapy by mask or nasal route	5
Hospitalized: illness severe	Inpatient; high flow oxygen therapy	6
	Intubation and mechanical ventilation, $pO2/FiO2 \geq 150$ or $SpO2/FiO2 \geq 200$	7
	Mechanical ventilation $pO2/FIO2 < 150$ ($SpO2/FiO2 < 200$) or vasopressors	8

	Mechanical ventilation pO ₂ /FiO ₂ <150 and vasopressors, dialysis, or ECMO	9
Deaths	Deaths	10

- SARS-COV-2 specific cellular and humoral immune response of severe and non-severe cases, measured by Luminex and ELISPOT.
- Induced immunity: Levels of antiviral cytokine release, measured by ELISA and flow cytometry, of peripheral blood monocytes (PBMC) from controls and patients with acute malaria infection (according to GE and RDT).

4.3. EXPLORATORY VARIABLES OF INTEREST :

- The proportion of patients infected with urinary and intestinal parasites.

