6. POPULATION OF ANALYSIS

6.1. ANALYSIS POPULATION PRIMARY

All enrolled participants will be included in the primary analysis.

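### The only check of control status can fall on study Day 5, so some controls who become severe later stay labelled non-severe in the primary comparison

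*Protocol*

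**What the plan says.** - **Timing of the check.** Protocol 5.2.2.1 heads the follow-up of controls "Day 7 +- 2: follow-up". Day 1 is the inclusion visit, so the window runs from Day 5 to Day 9. The text below the heading names Day 7 but is tentative: "a telephone contact on Day 7 with the treating clinician or the patient will be considered".
- **What the check decides.** "If, in the meantime, they have developed severe COVID-19, they will be excluded from the study", and they no longer count as controls.
- **Fallback.** "If no telephone contact is possible, a home visit by the control will take place at D7". Telephone numbers for the control, a relative and the physician are kept for monitoring health, but no later contact is scheduled.
- **Start of the clock.** Protocol 5.1.1 asks controls for "PCR-confirmed SARS-CoV-2 infection within 72 hours of inclusion". It sets no limit on time since symptom onset, and asymptomatic people are eligible.
- **SAP.** Section 4.2 scores controls once, at seven days of follow-up: "The clinical status of COVID-19 only controls is assessed by the WHO 10-point clinical progression score". Section 6.1 says "All enrolled participants will be included in the primary analysis". Table 1 of the SAP does not list progression to severe disease among the violations.
- **Severe patients.** Protocol 5.1.3 says "all severe cases in the care units of the selected centers will be investigated for their eligibility for the study".

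**The concern.** Case or control status is the outcome of the primary model (Protocol 7.1, SAP 7). The Protocol has decided that a control who becomes severe should not be analysed as a control, yet whether this is noticed depends on the day of the call. A control telephoned on Day 5 who deteriorates on Day 6 is kept. The same person telephoned on Day 8 is removed. Because days are counted from inclusion, someone enrolled soon after infection can be classed as finally non-severe early in the illness.

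If higher anti-CSP levels do go with milder disease, each retained converter moves the control distribution towards that of the cases. The estimated association shrinks and power falls. If there is no true association, there is nothing to dilute.

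**Working it through.** **Inputs (Protocol 5.1.5).** 100 cases and 200 controls, two per case; standard deviation of log anti-CSP 1 in both groups; case-control correlation 0.7; log means 6.80 (controls) and 6.61 (cases), so the difference is 0.19; two-sided 5% test; stated power 0.81 in the table and 80% in the text. I assume that the correlation of 0.7 also holds between the two controls of a set.

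**Reproducing the stated power.**
- Variance of case minus mean of two controls: 1 + (1 + 0.7)/2 − 2 × 0.7 = 0.45.
- Standard error with 100 sets: √(0.45/100) = 0.0671.
- Power: Φ(0.19/0.0671 − 1.96) = Φ(0.87) = 0.81.

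Simulated conditional logistic regression (10,000 data sets, Wald test) gives 0.80. The Protocol's figure is reproduced.

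**Effect of retained converters.** Let m be the share of retained controls who become severe after the check. The documents give no value for m, so it is an assumption. So is the premise that converters carry the full case mean. The expected difference is then 0.19 × (1 − m), and power is Φ(0.19(1 − m)/0.0671 − 1.96). The slight extra variance from mixing two kinds of control does not alter the two-decimal results.

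| m (assumed) | Converters among 200 | Log difference | Difference in medians | Power, formula | Power, simulated |
|---|---|---|---|---|---|
| 0 | 0 | 0.190 | 17.3% | 0.81 | 0.80 |
| 1% | 2 | 0.188 | 17.1% | 0.80 | 0.79 |
| 2% | 4 | 0.186 | 17.0% | 0.79 | 0.79 |
| 5% | 10 | 0.181 | 16.5% | 0.77 | 0.75 |
| 10% | 20 | 0.171 | 15.7% | 0.72 | 0.71 |

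By the formula, the loss exceeds two points only above about 2.6% (about 5 of 200 controls). Power drops below 0.75 at about 7%.

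**Effect of removing converters.** A set that loses one control becomes a 1:1 set, with variance 1 + 1 − 2 × 0.7 = 0.60. A set that loses both controls drops out. The information is 100 × [(1 − m)²/0.45 + 2m(1 − m)/0.60], and power is Φ(0.19 × √information − 1.96). At m = 5% the information is 100 × (0.9025/0.45 + 0.095/0.60) = 216.4, so power is Φ(0.19 × 14.71 − 1.96) = 0.80.

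| m (assumed) | Converters kept as controls | All converters removed |
|---|---|---|
| 2% | 0.792 | 0.805 |
| 5% | 0.767 | 0.798 |
| 10% | 0.721 | 0.786 |

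The right-hand column assumes complete detection, so it is an upper bound on what a later check could recover.

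**The case against.** The strongest reply is that Day 7 is the target throughout (Protocol text, fallback visit, SAP 4.2), that two days either way is an ordinary visit tolerance, and that any finite follow-up misses some later events. Much of this stands. The rates above are assumed, and they count every conversion after the check. Moving the window catches only conversions between an early call and Day 7, a subset that the documents do not allow one to size. A Day 7 to Day 9 window is still counted from inclusion, so it does not remove the dependence on stage of illness.

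Four stronger readings are tempting, and the documents do not support them.

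- **That a Day 5 call breaks a Day 7 rule.** The Protocol excludes controls who are severe by the time of the contact. It contains no separate rule about status on Day 7.
- **That power falls to 0.60.** With one control per case, as in SAP 5, and an assumed 100 pairs, power is Φ(0.19/√(0.60/100) − 1.96) = 0.69 before any conversion, and about 0.60 at 10%. The drop from 0.81 to 0.69 comes from the separate disagreement between Protocol and SAP on the matching ratio. Late conversion accounts only for the remaining 0.09.
- **That the same person will be analysed as both control and case.** Enrolment as a case would need a positive test no more than 72 hours old. Being screened does not by itself affect the analysis.
- **That controls are out of reach after the call.** Contact numbers are kept for health monitoring. What is missing is a scheduled check.

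What survives is that the single status check can be early, is worded as optional, and has no backstop. Separately, SAP 6.1 read literally would keep even detected converters in the primary analysis.

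**Conclusion.** The point holds as a limited weakness in how the control label is fixed. The direction of the bias is clear if the protective hypothesis is true: towards no difference. Its size cannot be settled from the documents. On the Protocol's own assumptions, and with converters carrying the case mean, the loss of power is one to two points at 1–2% late conversion, about four points at 5% and about nine at 10%. The first is minor. From about 5% it matters, because planned power has almost no reserve above 80%. The change is worth making because it applies the Protocol's own exclusion principle more evenly at little cost, not because the primary analysis is shown to be invalid.

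**What to change.** 1. **Protocol 5.2.2.1:** make the status contact definite rather than something to be considered, and set its window at Day 7 to Day 9. This keeps the single contact and the existing upper limit.
2. **Before database lock:** have authorised local investigators compare the control identification register with severe COVID-19 admissions at the four study centres, and apply the existing exclusion rule to any control found there.
3. **SAP 6.1:** reconcile it with Protocol 5.2.2.1, so that controls excluded for becoming severe are not analysed as controls in the primary model. Without this, the first two steps may not reach the primary result. State also what happens to a matched set that loses a control: with two controls the set can continue with one, but with one control it contributes nothing to the conditional likelihood.

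**Cost.** A narrower call window, one list comparison under the access restrictions of Protocol 5.2.2.1 and 8.4, and the loss of a few controls. No extra visit, call or sample is needed. Capture will be incomplete: Protocol 5.1 describes sixteen hospital centres in Kinshasa, and converters admitted outside the four study centres, or not admitted at all, will not be found.

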5.2.4 WITHDRAWAL AND TERMINATION OF THE STUDY

Participants may withdraw from the study at any time. This is the case if the participant or legal representative withdraws consent, or if the investigator considers that continuation of the study would have a negative effect on the patient's health.

Data and biological samples collected up to the time of the participant's withdrawal may be used for analysis purposes. However, if the participant expressly requests that they not be used, the data and samples will be destroyed.

6 DATA MANAGEMENT

6.1 DATA MANAGEMENT RESPONSIBILITIES

Although the principal investigator assumes ultimate responsibility for data management, practical implementation and monitoring will be carried out by the INRB data manager in collaboration with study staff at the sites. This will be done in accordance with the study's data management plan, which broadly describes the aspects below. The ITM Data Manager and other ITM colleagues will help support the implementation of this DMP.

6.2 DATA COLLECTION AND MANAGEMENT

6.2.1 DATA TYPES

Study data includes individual participant-level data at baseline and follow-up study visits. These include variables such as study participant identifiers, socio-demographic variables, medical history, symptoms, vital signs, laboratory results and final results status). See also 5.2.2.1 for further details.

6.2.2 COLLECTION AND MANAGEMENT METHODS

Study data will be collected on paper and/or directly via electronic questionnaires in the study database using REDCap. Only data defined by the study protocol will be collected.

REDCap (Research Electronic Data Capture) is a software application widely used in the academic research community to create and manage surveys, databases and research studies. It is a secure web application as well as a mobile application that can be used to collect, cleanse and manage subject information in compliance with various applicable standards and regulations (GCP, CFR 21 part 11, FISMA, HIPAA). Its mobile application enables offline data collection with smartphones or tablets. In addition, the software includes a query management system and capabilities for importing and exporting data in a variety of formats.

Paper questionnaires will be used where possible and appropriate. In addition, electronic questionnaires on tablets or laptops will be used to collect data from participants at remote sites. Subsequently, when connected to the Internet or cellular networks, data from the mobile device can be synchronized with the study server. Edit controls and branching logic, programmed on the electronic forms, will validate at the point of data entry and support data quality. To ensure better data quality, appropriate data management training will be organized before the actual data collection (and processing) begins. In addition, data will be

reviewed and monitored during the course of the study by various study collaborators to achieve timely database lock.

Because of the biological risk of COVID-19 contamination, any original written source document created at the patient's bedside (i.e. in the "red zone") should be treated as potentially infectious unless an effective means of decontamination can be instituted. Wherever possible, photographs, digital scans or other electronic data capture methods can be used.

6.3 DATA SECURITY AND CONFIDENTIALITY

The IT/data management system to be used incorporates a robust security architecture including encryption, firewalls, anti-virus software and controlled user access (tablet/computer authentication, REDCap username, personal password and authorized user role). Data backup will be provided at server, computer, mobile device and/or database level, where applicable.

ITM and INRB will also ensure that the necessary measures are taken to ensure the safekeeping of all data management documents (Data Management Plan, procedures, completed questionnaires) and that IT equipment (tablets, computers, server) is secured (locked cupboards, locked offices and/or rooms and/or controlled by badge).

Study participants' private data will be treated confidentially. Study participants' names and contact data will be replaced by an identification code specific to the study subject (= pseudonym). Only pseudonymized data will be used and distributed within the wider study team. See also 7.4 for further details.

6.4 DATA SHARING

The study will make its research data available for secondary research or to support the Congolese response to COVID-19 and considering the following key aspects:

- ITM's data sharing policy will be followed, with the following key aspects mentioned below
- The European FAIR data principles ("Findable"; "Accessible"; "Interoperable"; "Reusable") will also be respected ("as open as possible, as closed as necessary").
- Ensure confidentiality by anonymizing data (e.g. by replacing the study subject's identification code with a new code that can no longer be used to identify the patient; by generalizing and randomizing specific variables).
- Ensure that ethical approvals have been obtained by ethics committees and study participants.

PROTOCOL: MALARIA AS A PROTECTIVE FACTOR AGAINST SEVERE COVID-19 IN THE DEMOCRATIC REPUBLIC OF CONGO

- Making data available, mainly medical, personal and sensitive data, through a regulated data access mechanism and along a transparent decision-making process, with :
 - (i) Filling in a data request form,
 - (ii) Evaluation through access to committee data,
 - (iii) agreement to share data through this committee,
 - (iv) secure transfer of anonymized data,
 - (v) additional metadata that clarify the research data. Metadata will include study protocol, questionnaire(s), data dictionary.

6.5 RECORDING RETENTION

The principal investigator is responsible for the retention of all essential documents listed in the Good Clinical Practice guidelines: 'Informed Consent (Form)' or IC(F) or Formulaire de Consentement Eclairé. All essential documentation for all study subjects must be retained by the principal investigator in a secure storage facility for at least twenty years in accordance with INRB policies or local country regulatory requirements (whichever is longer). The DRC requires that study files be kept for up to 2 years after publication. These records must also be retained in accordance with the ethics committee's medical record retention requirements, whichever is longer. All stored records must remain confidential to the extent required by national, state and local laws of the jurisdiction in which they are stored.

